1 REVISION

Not applicable.

2 INTRODUCTION

Lung cancer is the most common malignancy in China. The main types include non-small cell lung cancer (NSCLC) and small cell lung cancer (SCLC). SCLC accounts for 10-15% of new lung cancers. As a highly aggressive neuroendocrine tumor, SCLC is significantly different from NSCLC clinically and pathologically, characterized by rapid growth, proneness to drug resistance, and early metastasis. Almost all patients with SCLC have a history of heavy tobacco use [9,10]. Traditionally, SCLC is classified into limited-stage disease (LD-SCLC, where tumor tissue surrounds a radiotherapy field) and extensive-stage disease (ED-SCLC, where tumor tissue exceeds the boundary of a radiotherapy field). Peripheral blood mononuclear cells (PBMCs) of patients with SCLC showed that those with a long survival have a high ratio of effector T cells to regulatory T cells [30]. Anti-PD-1 agents play a therapeutic role by blocking the binding of PD-L1 on tumor cells and PD-1 of T cells, blocking its inhibition on T cells. Compared with traditional cytotoxic chemotherapy, PD-1-targeted therapy has higher specificity, lower toxicity, and applicability to a variety of tumor types. Apatinib is a small-molecular targeted drug and exerts anti-angiogenesis effect to treat malignant tumors by inhibiting VEGFR. Hengrui conducted phase I/II clinical studies of the recombinant humanized anti-PD-1 monoclonal antibody injection (SHR-1210) in several tumor types of tumors, and preliminarily validated the safety, tolerability, and efficacy of SHR-1210 monotherapy in the treatment of advanced solid tumors. Considering the role of immune-related therapies in SCLC, as well as the role of immune checkpoint inhibitors combined with VEGF and VEGFR-2 inhibitors in patients with gastric cancer and renal cancer, the benefits from SHR-1210 combined with apatinib in the second-line treatment of SCLC are reasonable and worth looking forward to. Only topotecan (intravenously or orally administered) has been approved for the treatment of ED-SCLC after failure of first-line standard therapy by the FDA. No immunotherapy is commercially available currently. Preclinical data suggested that it has similar pharmacodynamics and anti-tumor effects to those of nivolumab and pembrolizumab. The studies on the PD-1/PD-L1-based combination therapy that have been published and ongoing abroad suggested that patients may benefit and the safety is controllable.

[figure not shown]
2.1 Study Design

This is a randomized, open-label, multi-center phase II clinical study. Eligible subjects after screening will be randomized into the following 3 groups in a 1:1:1 ratio, with 4 weeks as 1 treatment cycle. Refer to [Figure 1](#) for the study design. Refer to [Figure 2](#) for the study procedures.

The study consists of two stages. In Stage I, subjects will be randomized into 3 different dose groups, with 6 subjects in each group. It is planned that after the last subject in Stage I completes Cycle 1 treatment (28 days), the leading center's principal investigator and the sponsor will jointly perform a safety assessment of subjects enrolled in Stage I, decide the treatment group of Stage II, and choose one group of method of administration and a tolerated dose of apatinib for Stage II treatment.

A total of 39 subjects will be enrolled in Stage II. The primary analysis will be performed when the last subject has been treated for 180 days.

For any treatment group entering Stage II, if the safety is acceptable and the efficacy meets the corresponding statistical criteria, it indicates potential needs of further development.

Note: Subjects with PD for the first time must be confirmed; for medication after the first PD, refer to Section 6.1.2 of the protocol; for imaging confirmation and subsequent evaluations of the first PD, refer to Section 8.1.2 of the protocol

Figure 1. Design of the phase II study of SHR-1210 combined with apatinib

[figure not shown]

Figure 2. Study procedures of SHR-1210 combined with apatinib

2.2 Study Objectives

2.2.1 Primary objectives

- To evaluate the safety and efficacy of SHR-1210 combined with apatinib in the treatment of ED-SCLC after failure of the first-line standard therapy

2.2.2 Secondary objective

- To evaluate the immunogenicity

2.2.3 Exploratory objective

- To evaluate the correlation between biomarkers (including but not limited to PD-L1 and TMB) and efficacy

2.3 Sample Size

In this study, based on historical study data and study results of drugs of the same class and combined with clinical needs, a single-stage assessment method will be adopted to explore the efficacy of SHR-1210 combined with apatinib on ORR in ED-SCLC after failure of the first-line standard therapy.

Assume that in this study, it is expected that the ORR in each treatment group of SHR-1210 + apatinib combination therapy is $\geq 30\%$ (alternative hypothesis), and assume that there is no need to continue the study if the ORR is $\leq 15\%$ (null hypothesis), at the significance level of 0.1 and a power of 80%, 40 subjects should be enrolled. If ≥ 9 (22.5%) of the 40 subjects have response, it can be considered that the ORR in this treatment group is 15% and the investigational drug is worthy of continued development.

With a dropout rate of 10% taken into account, each treatment group should enroll about 45 subjects, for a total of 135 subjects.

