Study Treatment Discontinuation Criteria	Criteria for treatment discontinuation are as follows: 
1. Treatment discontinuation requested by subjects2. Radiographic or clinical evidence of progressive disease, unless the subject meets the criteria for continuing treatment beyond progression (see 6.1.2 of the protocol)3. Occurrence of pregnancy during the study4. Any clinical AEs, laboratory abnormalities, or other medical conditions indicating that the subject can no longer benefit from study treatment5. General deterioration of health status suggesting that the subject cannot continue to involve the study6. The enrolled subject is found to have important protocol deviations such as ineligibility7. Lost to follow-up

	
8. Termination by sponsor 9. Death 10. Other reasons as determined by the investigator

Determination of Sample Size	
Assume that in this study, the expected ORR in each treatment group of SHR-1210 + apatinib combination therapy is $\geq 30\%$ (alternative hypothesis), and that there is no need to continue the study if the ORR is $\leq 15\%$ (null hypothesis), at the significance level of 0.1 and a power of 80%, 40 subjects should be enrolled. If ≥ 9 (22.5%) of the 40 subjects have response, it can be considered that the ORR in this treatment group is 15% and the investigational drug is worthy of continued development.
 
With a dropout rate of 10% taken into account, each treatment group needs to enroll about 45 subjects. A total of 57 subjects are required in Stages I and II.

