3 STATISTICAL HYPOTHESIS

This study does not involve any statistical hypotheses and inference.

A single-stage assessment method will be adopted to explore the efficacy of SHR-1210 combined with apatinib on ORR in ED-SCLC after failure of the first-line standard therapy. The potential need for further development is indicated when the predefined number of responses (objective response) of a treatment group is reached (see Section 2.3 for details).

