6 INTERIM ANALYSIS

It is planned that after the 18th subject in Stage I completes Cycle 1 treatment (28 days), a safety analysis will be conducted. The leading center's principal investigator and the sponsor will jointly perform a safety assessment of subjects enrolled in Stage I and decide the treatment groups of Stage II.

This analysis only provides a listing of subjects' AEs and laboratory evaluations and does not involve the analysis of the efficacy endpoints.

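### SAP 2.3 plans a total of 135 subjects, but the design in SAP 2.1 sums to 57 and the protocol prints 57

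*SAP*

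**What the plan says.** SAP 2.3 takes 40 subjects as the number needed, allows 10% for dropout, and concludes that "each treatment group should enroll about 45 subjects, for a total of 135 subjects".

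SAP 2.1 describes the design. On Stage I it says: "In Stage I, subjects will be randomized into 3 different dose groups, with 6 subjects in each group". After a safety assessment, the leading center's principal investigator and the sponsor are to "choose one group of method of administration and a tolerated dose of apatinib for Stage II treatment". On the second stage it says: "A total of 39 subjects will be enrolled in Stage II". SAP 6 gives the size of Stage I independently, placing the safety analysis "after the 18th subject in Stage I completes Cycle 1 treatment".

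The protocol has the same two-stage design in its synopsis and section 4. Its sample-size text, in the synopsis and again in 10.1, is close to that of SAP 2.3 but ends differently: "A total of 57 subjects are required in Stages I and II". In both places the sentence just before that total also says that each treatment group needs about 45 subjects.

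**The concern.** The SAP contains two incompatible totals. One is printed in 2.3; the other follows from the components in 2.1 and agrees with the protocol. The planned sample size is a basic figure of any plan, and here a reader is sent to the section that has it wrong: SAP 3 says that further development is indicated "when the predefined number of responses (objective response) of a treatment group is reached (see Section 2.3 for details".

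Read by itself, SAP 2.3 describes three full-size groups, each able to be judged on its response count. Under the design in SAP 2.1 only the group taken forward reaches that size, and the other two are planned at 6 subjects each. Someone comparing enrolment with SAP 2.3 could also conclude that a trial that met its plan had fallen 78 subjects short.

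**Working it through.** Inputs:
- 40 subjects needed, 10% dropout, about 45 per group, total 135 (SAP 2.3). The 40 is taken as given here.
- 3 groups of 6 in Stage I, one group chosen, 39 subjects in total in Stage II (SAP 2.1; same in protocol section 4).
- 18 subjects in Stage I (SAP 6).
- Total 57 (protocol synopsis and 10.1).

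**Reproducing the SAP's figure.** 40 / (1 − 0.10) = 44.4, rounded up to 45. Then 3 × 45 = 135. The multiplication is correct, but it assumes that all three groups are enrolled to full size.

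**Total from the design.** Stage I: 3 × 6 = 18, which agrees with SAP 6. Adding Stage II: 18 + 39 = 57, which agrees with the protocol. SAP 2.1 does not print 57; it gives the parts.

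**Size of the gap.** 135 − 57 = 78, and 135 / 57 = 2.37. The 78 equals 2 × 39, the Stage II enrolment that the two groups not chosen would have needed. Put another way, 135 implies 135 − 18 = 117 = 3 × 39 subjects in Stage II, against 39 planned.

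**Where 45 belongs.** The group entering Stage II has 6 + 39 = 45, the same as 40 / 0.9 rounded up. The other two groups have 6 each, and 45 + 6 + 6 = 57. So 45 and 57 agree if 45 refers to one group. They do not agree if it refers to each group, which is how SAP 2.3, protocol 10.1 and the synopsis all word it.

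**If more than one group entered Stage II.** The 39 would be shared. Two groups would average 6 + 39/2 = 25.5 subjects and three groups 6 + 39/3 = 19. The total would still be 57, and no equal split would bring any group near 45.

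**The case against.** The best defence of 135 is that the documents do not describe the one-group design uniformly. SAP 2.1 also says "For any treatment group entering Stage II, if the safety is acceptable and the efficacy meets the corresponding statistical criteria", which leaves the number of groups open, and SAP 6 speaks of Stage II treatment groups in the plural. This stands as a criticism of the wording, and the correction should cover SAP 6. It does not rescue 135, because SAP 2.1 limits Stage II to 39 subjects in total however they are divided.

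A second defence is that enrolment is not fixed, since protocol 7.1.1 lets additional Stage I subjects be enrolled in certain circumstances. That stands too: 57 is a planned number and should be stated as such. But that provision is discretionary and case by case, and nothing in it plans for 78 more subjects.

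A third is that the SAP might record a deliberate later change. SAP 1 lists no revision, SAP 2.1 still carries the smaller design, and neither document explains 135.

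A fourth is that the matter is minor. Largely so: the response rate and its Clopper-Pearson interval are computed from the subjects in the analysis set (SAP 5.4.1), and no method in the SAP takes 135 as an input.

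Two stronger readings are tempting. A reader might infer that the protocol is right throughout and only the SAP needs correcting; but the protocol's two sample-size texts carry the same loose attribution of 45 to each group, directly before the total of 57. A reader might also infer that the trial needs 135 subjects and is under-enrolled at 57. The documents do not support this, because the design gives the group taken forward the 45 subjects that the calculation asks for.

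**Conclusion.** The total of 135 in SAP 2.3 is wrong for the design described. The planned total is 57, so the stated figure is 78 subjects, or 2.37-fold, too high. The conflict is within the SAP as well as between the SAP and the protocol. It is an inconsistency between sections, not a slip in multiplication.

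The conclusion that 135 conflicts with 57 rests only on figures printed in the documents. Assigning 45 to the group entering Stage II rests on one further reading: that the group's 6 Stage I subjects count toward the 45. No passage says so in terms for the response rate, but 6 + 39 matching the required 45 supports it. The 135-against-57 conflict does not depend on that reading.

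The effect is confined to the stated sample size. No estimate, interval or analysis set changes. It should be corrected because it is a basic planning figure and the correction is cheap.

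**What to change.** - **SAP 2.3:** replace the total of 135 with 57 planned subjects, made up of 18 in Stage I and 39 in Stage II, before any additional Stage I subjects allowed by protocol 7.1.1. In the same sentence, attach the figure of about 45 to the treatment group entering Stage II instead of to each group.
- **Protocol 10.1 and synopsis:** make the same change of attribution in the sentence that gives 45. The total of 57 stays.
- **SAP 6:** change the plural reference to Stage II groups to the singular, in line with the choice of one group in SAP 2.1.

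Two matters should stay out of this correction. The rule of 9 or more responses in 40 should not be restated here: its exact one-sided error rate at a 15% response rate is about 0.135, against the stated 0.1 if that level is one-sided, and this needs separate treatment. How to handle subjects if the apatinib regimen differs between stages is an analysis decision, not a wording change.

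The cost is one sentence in SAP 2.3, one phrase in two places in the protocol and one word in SAP 6. Design, enrolment and analyses are unchanged. The protocol edits need ethics committee submission under protocol 14.2, and the SAP edits should be made before database lock, as protocol 10.2 requires for the final SAP.

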3 STATISTICAL HYPOTHESIS

This study does not involve any statistical hypotheses and inference.

A single-stage assessment method will be adopted to explore the efficacy of SHR-1210 combined with apatinib on ORR in ED-SCLC after failure of the first-line standard therapy. The potential need for further development is indicated when the predefined number of responses (objective response) of a treatment group is reached (see Section 2.3 for details).

4.2 Secondary Endpoints

- Incidence of AEs and serious adverse events (SAEs) as per CTCAE V4.03, as well as laboratory measurements, ECG, vital signs, and other safety parameters
- Overall survival (OS): defined as the time from the first dose to the death of the subject of any cause.
- 6- and 12-month OS rates
- Progress-free survival (PFS): the time from the date of first dose to the first documented objective tumor progress as per RECIST 1.1 or death of any cause, whichever occurs first.
- Time to response (TTR): defined as the period of time from the date of first dose to the first documented tumor response (CR or PR). CR and PR must be evaluated per the RECIST 1.1 and confirmed for efficacy.
- Duration of response (DoR): the date from the first documented tumor response (CR or PR) to the first documented objective tumor progress (PD) or the date of death of any cause. Response defined by CR and PR must be assessed per the RECIST 1.1 and confirmed for efficacy. The start date of response duration is the first observed response, instead of the confirmed response.
- Disease control rate (DCR): defined as the proportion of enrolled subjects who are evaluated as CR, PR, or SD (for at least 4 weeks) per the RECIST 1.1. Response confirmation should be conducted for CR and PR.
- Immunogenicity evaluation: Positive rates of ADA and NAb

4.3 Exploratory Endpoint

- Tumor biomarkers (including but not limited to expression levels of PD-L1 and TMB in tumor samples)

5 STATISTICAL ANALYSIS

5.1 General Considerations

5.1.1 Analysis sets

The analysis sets in this study included:

Full analysis set (FAS): an analysis set determined based on the intent-to-treat principle. This analysis set includes all enrolled subjects who have received at least one dose of the study drug. Based on the FAS, the subjects will be analyzed according to their scheduled doses.

Per-protocol set (PPS): a subset of the FAS. Subjects with major protocol violations that have a major effect on the study results will be excluded from this set. The list of subjects included into or excluded from the PPS should be reviewed and determined by the sponsor and the investigator before the database is locked.

Safety set (SS): all subjects who have received at least one dose of the study drug and underwent post-administration safety evaluation. Analyses based on the safety set will be carried out according to the actual treatment received by the subjects.

ADA set (ADAS): All enrolled subjects who have received at least one dose of the study drug and have baseline and at least one post-baseline ADA evaluation data.

Tumor biomarkers set (TMKS): all enrolled subjects who have received at least one dose of the study drug and have tumor biopsy samples (including peripheral blood) make up the PD-L1 or TMB set.

Table X. Analysis sets and corresponding endpoints

Endpoint	Analysis Sets				
	FAS	PPS	SS	ADAS	TMKS
Safety Endpoints	X				
ORR	X	X			
OS and 6/12-month OS rates	X				
PFS	X				
TTR	X				
DoR	X				
DCR	X				
Immunogenicity Evaluation				X	
Tumor Biomarkers					X

5.1.2 General analysis

Unless otherwise specified, standard descriptive statistics will be summarized by different type of variables:

- Continuous variables will be summarized by mean, standard deviation, median, maximum, and minimum. The decimal places for the minimum and maximum should be consistent with those on the eCRF. There should be 1 additional decimal place for the mean and median compared to the raw data, and 2 additional decimal places for standard deviation, with up to 4 decimal places.
- Categorical variables will be summarized by frequency and percentage, with 1 decimal place for percentages;
- For time-to-event data, the Kaplan-Meier method will be used to estimate the survival function and median time to event onset, and the survival curves will be plotted.

If not otherwise specified, the baseline is generally defined as the last pre-administration observation before the first dose (including the day of administration). The last non-missing measurement value will be decided by the date of measurement. If there are multiple measurements on the same day, then:

- If both scheduled and unscheduled visits are present, the value obtained from the scheduled visit will be considered as the last non-missing measured value.
- If there are multiple scheduled visits, the value obtained from the visit with the largest visit number will be considered as the last non-missing measured value.
- If there is no scheduled visit but are multiple unscheduled visits, the value obtained from the visit with the largest number of unscheduled visit will be considered as the last non-missing measured value.

The date of first dose in this study is defined as the date of first dose of apatinib or the date of first dose of SHR-1210, whichever is earlier.

5.1.3 Derived variables

Not applicable.

5.1.4 Covariates and subgroups

Subgroup analysis of the primary endpoint ORR will be based on the FAS:

- Sensitive recurrence: progress in ≥ 90 days from the last chemotherapy
- Drug-resistant recurrence: progress during chemotherapy or within 90 days from the last chemotherapy

The time between progress and the last chemotherapy is calculated as follows: date of the most recent progress/relapse – date of the last chemotherapy. Sensitive recurrence is determined if the time between progress and the last chemotherapy is \geq 90 days; otherwise, drug-resistant recurrence is determined.

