5 STUDY POPULATION

5.1 Inclusion Criteria

Patients must meet all of the following inclusion criteria to be eligible for this study.

1. All patients must sign an ICF prior to starting any study-related procedures
2. Aged ≥ 18 and ≤ 70 years
3. Histologically or cytologically confirmed small cell lung cancer
4. Staged ED-SCLC according to VALG staging
5. Have previously received first-line platinum-based treatment for ED-SCLC and have shown objective imaging progression. Including:
 - Sensitive recurrence: progression in ≥ 90 days from the last chemotherapy
 - Drug-resistant recurrence: progression during chemotherapy or within 90 days from the last chemotherapy
6. Able to provide tumor tissue samples for diagnosis, either archived samples within 12 months prior to the first dose of study drug or freshly obtained. The specimens shall meet the requirements of formalin-fixed and paraffin-embedded (FFPE) tumor tissue blocks allowing the cutting of at least 5-10 slices with a thickness of 4-6 μm for staining and testing. Cell smears from fine needle aspiration or centrifuged pleural fluid, bone lesions without soft tissue components or decalcified bone tumor specimens, and drill biopsy tissues are not acceptable, as they are insufficient for biomarker detection
7. ECOG PS of 0-1
8. Life expectancy of ≥ 8 weeks
9. With at least one target lesion without previous radiotherapy (RECIST v1.1) shown by CT or MRI scan ≤ 28 days prior to the first dose of study drug
10. Males and females of reproductive potential must take contraceptive measures from the first dose of study drug to within 24 weeks after the last dose of study drug (see 6.6.2 of the protocol for recommended contraceptive methods)
11. Had no transfusion of blood or blood products within 14 days prior to the first dose, not corrected with G-CSF or other hematopoietic colony-stimulating factors. Before the first dose of study drug, laboratory test values must meet the following conditions:
 - (1) Hematology: $\text{WBC} \geq 3.0 \times 10^9/\text{L}$; $\text{ANC} \geq 1.5 \times 10^9/\text{L}$; $\text{PLT} \geq 100 \times 10^9/\text{L}$; $\text{HGB} \geq 9.0 \text{ g/dL}$

- (2) Liver function: AST $\leq 2.5 \times$ ULN, ALT $\leq 2.5 \times$ ULN for patients without liver metastasis; ALT and AST $< 5 \times$ ULN for patients with liver metastasis; TBIL $\leq 1.5 \times$ ULN (TBIL < 3.0 mg/dL in patients with Gilbert syndrome); and ALB ≥ 3 g/dL

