10.5.6 Subgroup analysis

The analysis of the primary endpoint ORR will be carried out in the following subgroups:

- Sensitive recurrence (progression in ≥ 90 days from the last chemotherapy)
- Drug-resistant recurrence (progression during chemotherapy or within 90 days from the last chemotherapy)

Other subgroup analyses will be detailed in SAP.

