5.2.2.2 Other baseline characteristics

The subjects' allergy, smoking, and alcohol history will be summarized and listed using descriptive statistics.

The diagnosis of small cell lung cancer in the subjects, including the VALG stage of the initial diagnosis, presence of metastases, course of disease, and time to the most recent progress/recurrence will be summarized using descriptive statistics. The course of disease (month) is defined as the time from the date of first pathological diagnosis to the date before the first dose, calculated as: (date of the first dose – date of the first pathological diagnosis) / 30.4375. The time to the most recent progress/recurrence (month) is defined as the time from the most recent progress/recurrence to the date before the first dose, calculated as: (date of the first dose – date of the most recent progress/recurrence) / 30.4375. The date of the first diagnosis, location of the primary tumor, location of the metastasis, diagnostic method, the VALG stage of the first diagnosis, date of the most recent progress/recurrence, course of the disease, and time to the most recent recurrence/progress will be listed.

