5.4.4 Subgroup analysis

Based on the FAS, the following subgroup analyses will be performed on the primary efficacy endpoint ORR, as well as the secondary endpoints OS, PFS, and 6/12-month OS rates:

- Sensitive recurrence: progress in \geq 90 days from the last chemotherapy
- Drug-resistant recurrence: progress during chemotherapy or within 90 days from the last chemotherapy

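### SAP 5.1.4 dates relapse from the most recent progression, so a subject who first progressed on or soon after chemotherapy and progressed again at 90 days or later is labelled sensitive against the SAP's own definition

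*SAP*

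**What the plan says.** Protocol 5.1, criterion 5, admits subjects who "Have previously received first-line platinum-based treatment for ED-SCLC and have shown objective imaging progression" and names two kinds of relapse. The second is "Drug-resistant recurrence: progression during chemotherapy or within 90 days from the last chemotherapy"; the first is progression 90 days or more after the last chemotherapy. Protocol 10.5.6 uses the same split for the ORR subgroups, describing the resistant group as "progression during chemotherapy or within 90 days from the last chemotherapy".

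SAP 5.1.4 repeats both definitions as bullets and then gives the derivation. The time between progression and last chemotherapy is "calculated as follows: date of the most recent progress/relapse" minus the date of the last chemotherapy. At 90 days or more the subject is sensitive; "otherwise, drug-resistant recurrence is determined". Nothing says what to do when a subject has more than one progression after the last chemotherapy.

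SAP 5.4.4 restates the resistant group as "Drug-resistant recurrence: progress during chemotherapy or within 90 days from the last chemotherapy" and applies the split to ORR, OS, PFS and the 6- and 12-month OS rates. It is the only subgroup pair in the SAP. Among progression dates, SAP 5.2.2.2 lists only the "date of the most recent progress/recurrence".

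**The concern.** The definition asks whether the disease progressed on chemotherapy or soon after it. The formula asks how long after chemotherapy the latest progression was recorded. For a subject with one progression these are the same question. For a subject with two or more they need not be, and the formula then discards the early progression that met the resistant definition.

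The entry criteria allow such subjects. Criterion 5 limits neither the number of progressions nor the time from progression to enrolment. Treatment other than chemotherapy before entry is foreseen: protocol 5.2 refers to earlier chest and whole-brain radiotherapy and to treated brain metastases, and protocol 5.1, criterion 9, asks for a target lesion that has not been irradiated, which implies that other lesions may have been. An early relapse, local treatment, and a further progression past day 90 is therefore a possible route into the trial.

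At stake is the meaning of the sensitive subgroup. With the last chemotherapy date fixed, a later progression date can only lengthen the interval, so any mislabelling adds resistant subjects to the sensitive group and never the reverse.

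**Working it through.** No stated sample size, power or error rate depends on this rule, so there is no figure of the plan to reproduce. The check is to apply the rule to dated cases and then bound its effect.

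**1. Formula against definition.** Days are counted from the last chemotherapy dose. The SAP label uses the most recent progression; the comparison label uses the first progression on or after the start of the last chemotherapy regimen. Both cut at 90 days.

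| Case | Progressions (day) | First | Most recent | By first progression | By SAP formula |
|---|---|---|---|---|---|
| A | 60 | 60 | 60 | resistant | resistant |
| B | 60, then 120 | 60 | 120 | resistant | **sensitive** |
| C | 40, then 80 | 40 | 80 | resistant | resistant |
| D | −10 (on chemotherapy), then 100 | −10 | 100 | resistant | **sensitive** |

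A further case has a progression at day 60, new chemotherapy with its last dose at day 100, and progression at day 130. The new chemotherapy resets the clock, both rules give 130 − 100 = 30 days, and both say resistant.

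Only B and D change. A move needs all three of:
- a first progression during the last chemotherapy or less than 90 days after it;
- a further progression recorded before study entry at 90 days or later;
- no chemotherapy between the two.

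**2. How many subjects.** The documents give no frequency, so this is an illustration on assumptions. Let N be 45 (6 + 39, the selected regimen) or 57 (18 + 39, the planned total), let 40–60% be truly resistant, and let 0–20% of those meet all three conditions. Subjects moved = N × resistant share × fraction meeting the conditions.

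- Lower end: 0.
- Upper end, N = 45: 45 × 0.60 × 0.20 = 5.4.
- Upper end, N = 57: 57 × 0.60 × 0.20 = 6.8.
- Share of the labelled sensitive group that is really resistant, upper end, N = 45: 5.4 / (18 + 5.4) = 23%. The share is the same for N = 57.

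**3. Effect on subgroup ORR.** Assume true ORRs of 40% (sensitive) and 20% (resistant). At the upper end with N = 45, the labelled sensitive ORR is (0.40 × 18 + 0.20 × 5.4) / 23.4 = 35.4%. At the lower end it stays at 40%.

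**4. A small worked example.** Take 45 subjects: resistant 5/25 = 20.0%, sensitive 8/20 = 40.0%, gap 20.0 points. Move three resistant subjects.

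- If they respond at the resistant rate (0.6 expected responses): 4.4/22 = 20.0% and 8.6/23 = 37.4%, gap 17.4 points.
- If none responds: 5/22 = 22.7% and 8/23 = 34.8%, gap 12.1 points.
- If all three respond: 2/22 = 9.1% and 11/23 = 47.8%, gap 38.7 points.

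The label error runs one way. Its effect on the gap in a single trial depends on who moves; in expectation the gap narrows, by 2.6 points here.

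**5. Against sampling error.** The exact 95% interval is 19% to 64% for 8/20 and 7% to 41% for 5/25. The expected shift is well inside both.

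**The case against.** The strongest reply is that neither the protocol nor the SAP says first progression. A subject who progressed at day 60 and again at day 120 literally has a progression in each window, so the formula could be seen as settling an ambiguity. Pairing the most recent relapse with the last chemotherapy also has a sound purpose: for subjects with several earlier regimens, which SAP 5.2.4.1 foresees, it avoids using a progression from before the last regimen.

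The purpose is sound, but the formula does not serve it fully. If the two categories are to be exclusive, the definition works only when the early progression decides; a subject who progressed on chemotherapy does not stop having done so because the disease progressed again later. The first progression on or after the start of the last regimen keeps the pairing and respects the definition.

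It is also fair that the route is narrow. It needs a subject with ECOG 0–1 to go past day 90 after an early relapse without further chemotherapy, in a disease the protocol describes as fast growing. That limits the number but does not exclude it.

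Three stronger inferences are not supported:
- A reader might infer that every resistant subject who progresses again is relabelled. Case C and the case with new chemotherapy show otherwise.
- A reader might infer that the screening scan could itself become the most recent progression. The documents treat that scan as the baseline tumour evaluation and do not say that it replaces the recorded relapse date.
- A reader might expect a large loss of contrast. The 12.1-point gap above requires all three moved subjects to be non-responders.

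**Conclusion.** The formula in SAP 5.1.4 can contradict the definition directly above it, and those in SAP 5.4.4 and protocol 5.1 and 10.5.6. The contradiction is confined to subjects who meet the three conditions above, and it runs only from resistant to sensitive. It is a stated rule that gives the wrong label for these subjects, which makes it more than a missing detail.

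The size is unknown and probably small. The 0 to 5.4 of 45 (or 0 to 6.8 of 57) rests wholly on the assumed shares, and the ORR shifts on assumed response rates.

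A reader might go on to infer that the trial's main conclusion is at risk. It is not. The FAS ORR and the criterion of at least 9 responses in 40 count all responders in a treatment group whatever their relapse type. Both types are eligible, so entry is unaffected. The plan disclaims formal inference, and these subgroup results are descriptive. The case for correcting it is that this is the only subgroup pair the plan specifies and the correction is cheap.

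**What to change.** In SAP 5.1.4, calculate the interval as the date of the first documented progression on or after the start of the last chemotherapy regimen, minus the date of the last chemotherapy dose. Class any progression during that regimen, or at less than 90 days, as resistant, and 90 days or more as sensitive. Subjects with a single progression in that period keep their label.

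Before database lock, confirm that this date is available. If the eCRF holds only the most recent progression date, collect the first one from the medical record. The check can be limited to subjects whom the present formula calls sensitive: if the most recent progression is under 90 days, an earlier one is too, and the label cannot change.

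The cost is about one sentence in the SAP and at most one extra date for those subjects. The documents do not describe the eCRF field, so the retrieval effort cannot be stated exactly, but it should be small.
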